13.2 SAP Amendment 4 changes

The main rationale for SAP Amendment 4 is to include details on the additional key derived and component exploratory variables required based on the results from the analyses of historical tumor biopsy samples in Part A. It was decided that these additional variables were needed to improve the interpretability of the test results received from the laboratory. Note that there have not been any tumor biopsies performed at Screening or at Cycle 1 Day 22 in Part A. Per protocol, these tumor biopsies are optional in Part A and only samples available from historical tumor biopsies have been sent to the laboratory and analyzed to date. This SAP amendment also provides some clarifications relating to the handling of data for the purpose of summarizing safety and exploratory anti-tumor activity endpoints.

The key changes are summarized in the table below (note that additional minor corrections and clarifications were also applied in this amendment but are not included in this table).

Section	Description of Change
1	The versions and dates of supporting study documentation were updated.
3.5.7	The definition of the DLT Evaluable Set (DES) was included in this section consistent with the latest version of the protocol.
5.1	An update was made to the example illustrating the definition of a complete cycle of UCB6114.
8.1	The additional summary of the total number of doses of study treatment received was included.
8.2	Rules for handling missing relationship to study treatment for an adverse event were updated.
8.4.2	Clarification on the handling of triplicate ECG measurements was included.
9.2	Details on the analysis of the historical tumor biopsy samples was included together with rules for defining key and component derived variables based on the test results received from the laboratory. These variables were considered important for clearer interpretation of these results from data listings.
9.3	A predefined fold-increase of 1.80 was included.

Section	Description of Change
10.1.2	Rules for applying the protocol-defined window around the post-Baseline tumor assessments (scheduled and unscheduled) for the purpose of summarizing the investigator's overall tumor response assessment were included.
General	MedDRA® version number was updated to the latest version (25.1) throughout the document.

This document cannot be used to support any marketing authorization application and any extensions or variations thereof.
PUBLIC COPY

CDISC	Clinical Data Interchange Standards Consortium
CDMS	clinical data management system
cGremlin-1	circulating gremlin-1
CI	confidence interval
COVID-19	coronavirus disease 2019
CPPC	CDMS postproduction change
CR	complete response
CS	clinically significant
CRC	colorectal adenocarcinoma
CRO	contract research organization
CSR	clinical study report
ctDNA	circulating tumor deoxyribonucleic acid
CTMS	clinical trial management system

DCR	disease control rate
DEM	data evaluation meeting
DES	DLT evaluable set
DLT	dose limiting toxicity
DOR	duration of response
ECG	electrocardiogram
ECOG	Eastern Cooperative Oncology Group
eCRF	electronic case report form
EMA	European Medicines Agency
ES	enrolled set
EudraCT	European Union Drug Regulating Authorities Clinical Trials
FAP	fibroblast activation protein
FDA	Food and Drug Administration
GCP	good clinical practice
GEJ	gastroesophageal junction
geoCV	geometric coefficient of variation
geoMean	geometric mean
H & E	hematoxylin and eosin
hh:mm	hours:minutes
HLT	high level term
ICH	International Council for Harmonization
IHC	immunohistochemistry
IM	invasive margin
iv	intravenous
IPD	important protocol deviations
LLOQ	lower limit of quantification
LLT	lowest level term
LoT	list of TFLs

LVEF	left ventricular ejection fraction
MedDRA®	Medical Dictionary for Regulatory Activities
MRD	minimum required dilution
n	number of study participants
NCI CTCAE	National Cancer Institute Common Terminology Criteria for AEs
NC	not calculable
NCS	not clinically significant
NEst	not estimable
NV	no value
ORR	objective tumor response rate
OS	overall survival
PCS	potentially clinically significant
PD	pharmacodynamic(s)
PDILI	potential drug-induced liver injury
PDS	pharmacodynamic set
PK	pharmacokinetic(s)
PKS	pharmacokinetic set
PFS	progression-free survival
PPS	per-protocol set
pSMAD1/5/8	phosphorylated mothers against decapentaplegic homolog 1/5/8
PR	partial response
PT	preferred term
PTEN	phosphatase and tensin homolog
Q2W	every 2 weeks
Q3W	every 3 weeks
Q4W	every 4 weeks
QTcF	QT interval corrected for heart rate using Fridericia's formula
RECIST	Response Evaluation Criteria in Solid Tumors

This document cannot be used to support any marketing authorization application and any extensions or variations thereof.

SAE	serious adverse event
SAP	statistical analysis plan
SD	stable disease
SDTM	Study Data Tabulation Model
SFU	safety follow-up
SI	International System of Units
SMAD4	mothers against decapentaplegic homolog 4
SMC	Safety Monitoring Committee
SoC	standard of care
SOC	system organ class
SS	safety analysis set
TEAE	treatment-emergent adverse event
TEMA	treatment-emergent markedly abnormal
TFL	Table, Figure and Listing
TNM	TNM Classification of Malignant Tumors
TPS	tumor proportion score
UK	United Kingdom
ULN	upper limit of normal
US	United States
WHODD	World Health Organization Drug Dictionary

1 INTRODUCTION

The purpose of this statistical analysis plan (SAP) is to provide all information that is necessary to perform the required statistical analysis of the dose optimization module (Part A1) of study ONC001. Separate SAPs are available for the other parts of the study. This SAP also describes the summary tables, figures and listings (TFLs) to be generated for Part A1 according to

Protocol amendment 6, dated 26 JUN 2023,

Electronic case report form (eCRF) (Clinical Data Management System [CDMS] postproduction change [CPPC] #14, Version 23.0, dated 14 APR 2023),

UCB's standards for TFL shells Version 2023Q1,

Part A TFL shells Final Version 2.4, dated 4 JUL 2023,

Part A1 TFL shells Final Version 2.0, dated 25 JUL 2023,

ONC001 Derivation of Efficacy Endpoints Version 0.6, dated 21 JAN 2022.

Unless specified in the sections below, Part A1 of the study will be analyzed as described in the most recent version of the protocol. If a future protocol amendment necessitates a substantial change to the analysis of the Part A1 study data, this SAP will be amended accordingly. In addition, if the methodology for the analysis of key study endpoints must be modified or updated prior to the final database lock for Part A1 of this study, a SAP amendment will be required. Protocol amendments that do not affect the statistical analysis will not necessitate an amendment to the SAP. If, after database lock, additional analyses are required to supplement the planned analyses described in this SAP, these changes will be described in the clinical study report (CSR) together with the associated rationale.

Note that there may be a number of data cut-offs defined prior to the final database lock for Part A1 due to the regulatory safety reporting requirements for this study.

The content of this SAP is compatible with the International Council for Harmonization (ICH)/Food and Drug Administration (FDA) E9 Guidance.

UCB is the Sponsor and ICON PLC is the contract research organization (CRO) for this study.

2 PROTOCOL SUMMARY

2.1 Study objectives

2.1.1 Primary objective

The primary objective of Part A1 (dose optimization module) of this study is to characterize the safety profile of UCB6114 administered as monotherapy in study participants with unresectable locally advanced or metastatic colorectal adenocarcinoma, gastric adenocarcinoma, adenocarcinoma of the gastroesophageal junction, or pancreatic adenocarcinoma.

2.1.2 Secondary objective

The secondary objective of Part A1 of this study is to characterize the pharmacokinetics (PK) of UCB6114 administered as monotherapy in study participants with unresectable locally advanced or metastatic colorectal adenocarcinoma, gastric adenocarcinoma, adenocarcinoma of the gastroesophageal junction, or pancreatic adenocarcinoma.

2.1.3 Exploratory/Tertiary objectives

The exploratory/tertiary objectives of Part A1 of this study are:

- To document any antitumor activity observed with UCB6114 administered according to relevant Response Evaluation Criteria in Solid Tumors (RECIST) criteria;
- To explore pharmacodynamics (PD) biomarkers of UCB6114;
- To evaluate the incidence, emergence, and impact of anti-drug (UCB6114) antibody (ADA) activity.

2.2 Study endpoints

2.2.1 Safety endpoints

2.2.1.1 Primary safety endpoints

The primary endpoints for Part A1 of this study are for safety, specifically the incidence and severity of treatment-emergent adverse events (TEAEs) (including serious adverse events [SAEs]) from the first dose of UCB6114 on Day 1 of Cycle 1 to the Safety Follow-up (SFU) visit, and the incidence of dose limiting toxicities (DLTs) from the first dose of UCB6114 on Day 1 of Cycle 1 to the end of the 28-day DLT Observation Period for all cohorts.

2.2.1.2 Other safety endpoints

The following other safety data will be assessed during Part A1 of the study to further support the characterization of the safety profile of UCB6114 administered as monotherapy:

- Clinical laboratory data (hematology, serum chemistry, coagulation and urinalysis);
- Vital signs (systolic and diastolic blood pressure, pulse rate, respiratory rate, and body temperature);
- 12-lead electrocardiogram (ECG);
- Echocardiogram (left ventricular ejection fraction [LVEF]);
- Eastern Cooperative Oncology Group (ECOG) performance status;
- Physical examination.

2.2.2 Pharmacokinetic and pharmacodynamic endpoints

2.2.2.1 Secondary pharmacokinetic endpoint

The secondary endpoint in Part A1 of this study is for PK, specifically UCB6114 concentration by scheduled assessment for each UCB6114 dose schedule cohort.

2.2.2.2 Exploratory pharmacokinetic endpoints

██████████ will be exploratory PK endpoints in Part A1.

2.2.2.3 Exploratory pharmacodynamic endpoints

The following exploratory PD endpoints will be assessed in Part A1 and reported separately outside of the CSR:

- Change in transcriptional and protein marker levels in blood and tumor tissue by scheduled assessment/timepoint and for each UCB6114 dose schedule cohort.
- Change in circulating tumor deoxyribonucleic acid (ctDNA) levels in blood by scheduled assessment and for each UCB6114 dose schedule cohort.

2.2.2.4 Exploratory immunogenicity endpoints

Immunogenicity in Part A1 will be explored using ADA sample status and participant classification, and changes in titer over time. Potential relationships between ADA and PK, PD, anti-tumor activity and safety may also be explored but these analyses will be reported separately outside of the CSR.

2.2.3 Efficacy endpoints

2.2.3.1 Exploratory antitumor activity endpoints

Antitumor activity in Part A1 will be explored using the following endpoints:

- Objective tumor response rate (ORR);
- Disease control rate (DCR);
- Duration of antitumor response (DOR);
- Progression-free survival (PFS);
- Overall survival (OS).

2.2.3.2 Other exploratory efficacy endpoint

To further explore efficacy in Part A1 of the study, changes from Baseline in the ECOG performance status scale will be assessed.

2.3 Study design and conduct

Study ONC001 is a multicenter, nonrandomized, open-label, Phase 1/2 study evaluating the safety, PK, efficacy (as assessed by antitumor activity), PD, biomarkers, and immunogenicity (ADA activity) of intravenous (iv) UCB6114 as monotherapy and in combination with selected standard of care (SOC) regimens in study participants with advanced solid tumors.

The study has a modular design including up to 3 dose escalation modules (Parts A, B, and C), 1 dose optimization module (Part A1), and up to 4 dose expansion modules (Parts D, E, F, and G). Depending on emerging data, not all modules may open. This SAP is focused only on the dose optimization module of the study to evaluate alternative dosing schedules for UCB6114 administered as monotherapy in participants with unresectable locally advanced or metastatic colorectal adenocarcinoma, gastric adenocarcinoma, adenocarcinoma of the gastroesophageal junction, or pancreatic adenocarcinoma.

Part A1 consists of a Screening Period, Treatment Period (consisting of 28-day cycles for Cohorts 1, 2, and 4, and of 21-day cycles for Cohort 3), a SFU visit and a Final Visit. During the Treatment Period, UCB6114 will be administered as iv infusion as per the defined dosing

schedules in Table 6-6 of the protocol until the occurrence of progressive disease, unacceptable toxicity, or withdrawal of consent.

Part A1 will be initiated after Cohort 5 of Part A (2000mg every 2 weeks [Q2W]) has been determined to be safe (i.e. DLT incidence <33%, see Section 4.1.2.4 of the protocol). Eligible participants with unresectable locally advanced or metastatic colorectal adenocarcinoma, gastric adenocarcinoma, adenocarcinoma of the gastroesophageal junction, or pancreatic adenocarcinoma will receive iv infusion of UCB6114 as monotherapy.

[figure not shown]
The planned dose optimization scheme for Part A1 will assess the safety and tolerability of the new drug formulation and will explore shortening of the infusion time and less frequent dosing as follows:

- Cohort 1: 2000mg Q2W (60-minute iv infusion), 28-day treatment cycle
- Cohort 2: 2000mg Q2W (30-minute iv infusion), 28-day treatment cycle
- Cohort 3: 3000mg every 3 weeks (Q3W) (90-minute iv infusion), 21-day treatment cycle
- Cohort 4: 4000mg every 4 weeks (Q4W) (120-minute iv infusion), 28-day treatment cycle

Up to 32 participants will be allocated 1:1:1:1 to one of the 4 cohorts, with each cohort enrolling up to 8 study participants including 1 sentinel participant with an observation period of 48 hours. The enrollment of a sentinel participant in each cohort has been included as an additional risk mitigation measure to monitor infusion related reactions and other early onset treatment-related AEs.

The planned duration of study treatment is 2 cycles. Participants may, however, remain in the study for additional cycles if they are receiving therapeutic benefit (stable disease [SD], partial response [PR], or complete response [CR]) or until they fulfill one of the criteria for study treatment discontinuation. Participants will continue study treatment until disease progression, unmanageable toxicity, or withdrawal of consent. Upon discontinuation from study treatment, participants will be referred to appropriate follow-up care per the investigator's judgment.

A schematic diagram of Part A1 of the study is provided in [Figure 2-1](#).

Figure 2-1: Study Schematic for Part A1

* Cohorts 1, 2, and 4: 28-day treatment cycles; Cohort 3: 21-day treatment cycles

D=day; iv=intravenous; Q2W=every 2 weeks; Q3W=every 3 weeks; Q4W=every 4 weeks

A Safety Monitoring Committee (SMC) will convene after each sentinel participant is assessed for at least 48 hours following the first administration of UCB6114 in the first cycle of a cohort to determine whether further participants within the cohort can be enrolled. The SMC will also convene after 25%, 50% and 100% of study participants in Part A1 have completed the required 28-day DLT Observation Period. If deemed necessary, an additional SMC meeting can convene after 75% of the participants have completed the required 28-day DLT Observation Period. If 1 or more DLTs are reported for a cohort then an *ad hoc* SMC will convene to determine if the dosing schedule and study module can continue as planned.

After consultation, the SMC will provide recommendations which could include an expansion of enrollment in a particular cohort to gain additional safety data, continuation of Part A1 with modifications or a temporary suspension of enrollment in a particular cohort. Details are described in the Part A1 SMC Charter.

2.4 Determination of sample size

In Part A1, up to 32 eligible participants will be enrolled across 4 alternative dosing schedules; 8 participants per cohort is considered sufficient to protect against an unacceptable level of toxicity. The probability of declaring a dose schedule (cohort) too toxic, given a toxicity rate greater than the maximum tolerable toxicity rate (33%) is approximately 90%. However, the probability is reduced to 80% when the dose optimization module is considered independent of Part A. An administrative decision to stop enrolling into Part A1 may be made by the Sponsor at any time.

3 DATA ANALYSIS CONSIDERATIONS

3.1 General presentation of summaries and analyses

All TFLs will be produced by ICON PLC using SAS® Version 9.4 or higher (SAS Institute, Cary, North Carolina, USA). ICON PLC will also produce the analysis datasets which will adhere to the Clinical Data Interchange Standards Consortium (CDISC) guidance documents for Analysis Data Model (ADaM) and follow UCB's interpretation. General statistical and reporting conventions will follow the current UCB Global Conventions Document Version 1.1.

Data will be summarized by UCB6114 dose schedule cohort (treatment group), visit and timepoint, as applicable. All relevant reported and derived data will be listed and will be presented by treatment group, study participant and visit, as applicable.

Categorical variables will be summarized using frequency counts and percentages. Unless otherwise stated, the denominator for the percentages will be based on the number of participants in the respective analysis set, treatment group, visit and timepoint (as applicable) with non-missing data.

When reporting frequency counts and percentages, the following rules apply:

- For categories where all participants fulfill certain criteria, the percentage value will be displayed as 100;
- For categories where zero participants fulfill certain criteria, there will be no percentage displayed;
- All other percentage displays will use 1 decimal place.

Summary statistics will be presented for continuous variables including number of participants (n), arithmetic mean, standard deviation, median, minimum and maximum. 95% confidence intervals (CIs) for the arithmetic mean may also be included depending on the variable and where stated in the SAP. Geometric mean (geoMean), geometric coefficient of variation (geoCV) and 95% CI for the geoMean will also be presented in the summaries of UCB6114 concentration data. In all relevant outputs the 95% confidence limits will be restricted to the possible values that the variable can take.

When reporting descriptive statistics for data other than UCB6114 concentration data, the following rules will apply:

- n will be an integer;
- Mean (arithmetic and geometric), standard deviation, median and quartiles will use 1 decimal place more, or 1 significant figure more – depending on the reporting format of the original data – than the original data. Original data may be data as reported directly onto the eCRF or summary data based on data reported onto the eCRF (e.g. mean of triplicates or percentage change from Baseline);
- Confidence intervals will be presented to the same number of decimal places as the value around which the CI is constructed;
- Minimum and maximum will be reported using the same number of decimal places or significant figures as the original value;

- A minimum of 3 values are required to calculate summary statistics. If only 2 values are available, then these should be presented as the minimum and maximum with other summary statistics reported as missing (“- “); if no participants have data at a given timepoint, then only n=0 will be presented;
- Percentage change from Baseline values will be calculated and displayed to 1 decimal place in the listings. In the summaries, where applicable, the mean, standard deviation and median percentage change from Baseline values will be presented to 2 decimal places and the minimum and maximum values presented to 1 decimal place.

[figure not shown]
When reporting individual UCB6114 concentration data in listings and figures, and presenting summary statistics in tables, the following rules will apply:

- UCB6114 concentration data should be reported in the listings to the same level of precision as received from the bioanalytical laboratory;
- Missing data should be reported as ‘NV’ (no value) in the listings;
- Concentrations below the lower limit of quantification (LLOQ) should be reported as BLQ (below the limit of quantification) in the listings;
- BLQ values prior to C_{max} should be set to 0 for purposes of plotting a figure (to capture lag-time);
- Actual sampling times will be used in the spaghetti plots of individual PK concentrations over time, and nominal sampling times will be used in the summaries of geoMean concentrations over time;
- UCB6114 concentration data should be plotted on both linear and semi-logarithmic scales;
- To calculate summary statistics, BLQ values should be set to half the LLOQ value and missing values should be excluded;
- When the total number of BLQ and missing values exceeds one third of the total then only minimum and maximum should be reported for this timepoint. Other summary statistics should be reported as missing (“- “). The minimum should be reported as BLQ;
- When the mean value includes one or more replaced BLQ values then a footnote should be included to say “contains one or more BLQ values replaced by half the LLOQ value”;
- A minimum of 3 values are required to calculate summary statistics. If only 2 values are available, then these should be presented as the minimum and maximum with other summary statistics reported as missing (“- “); if no participants have data at a given timepoint, then only n=0 will be presented;
- Summary statistics for UCB6114 concentration data will be reported to the same level of precision as the individual data for the minimum and maximum, and to 1 additional decimal place or 1 additional significant figure – depending on the reporting format of the original data with a maximum of 3 significant figures - for the mean (arithmetic and geometric), median and standard deviation. The 95% CI for the geoMean will use the same number of decimal places or significant figures as the geoMean. It will be left blank if the geoCV is 0;

- Geometric coefficient of variation will be reported as a percentage to 1 decimal place. The geoCV will be calculated using the following formula where SD is the standard deviation from the log-transformed data:

$$GeoCV(\%) = \sqrt{\exp SD^2 - 1} \times 100$$

When reporting PK parameters in listings and figures, and presenting summary statistics in tables, the following rules will apply:

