4.4 Safety laboratory data

The rules for handling values that are BLQ in the safety laboratory data will be the same as those described for PK data in [Section 3.1](#). Any values above the limit of quantification (ALQ) will be assigned as the value of upper limit of quantification.

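### The one-third rule for UCB6114 concentration tables counts missing samples with BLQ samples and then prints the minimum as BLQ even if no sample was BLQ

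*SAP*

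**What the plan says.** The list of rules for UCB6114 concentration data in Section 3.1 is the same, on this point, in the Part A and Part A1 SAPs.

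- **Calculation:** "BLQ values should be set to half the LLOQ value and missing values should be excluded".
- **Display threshold:** "When the total number of BLQ and missing values exceeds one third of the total then only minimum and maximum should be reported" for the timepoint. The other statistics become a dash, and "The minimum should be reported as BLQ".
- **Sparse data:** "A minimum of 3 values are required to calculate summary statistics". If there are only two values, those two are shown as minimum and maximum.
- **Listings:** a missing concentration is shown as NV and one below the LLOQ as BLQ, so the plan itself treats these as different states.

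Section 3.1 also says that concentration summaries carry the geoMean, geoCV and 95% CI. The secondary PK endpoint in Part A1 (Section 2.2.2.1) is "UCB6114 concentration by scheduled assessment for each UCB6114 dose schedule cohort". Part A has the equivalent endpoint by dose.

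For safety laboratory data, Section 4.2.2 (Part A) and Section 4.4 (Part A1) say: "The rules for handling values that are BLQ in the safety laboratory data will be the same as those described for PK data", with a reference back to Section 3.1.

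**The concern.** A sample that was not drawn, was lost or gave no result says nothing about the assay limit. The threshold nevertheless adds it to the BLQ samples, and the sentence on the minimum then assumes that at least one BLQ sample exists. When missing samples alone pass the threshold, that assumption is false. The table then shows BLQ where every measured sample was quantifiable, and a reader would take it that drug was undetectable in someone. The by-participant listing would contradict the table.

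The second effect is loss of information. Cohorts are small, so a few absent samples remove the geoMean and its interval from a timepoint that still has enough measured values to summarize. The secondary PK endpoint is defined timepoint by timepoint, so this is where the loss falls.

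**Working it through.** The plan states no figure that depends on this rule, so there is nothing to reproduce. The check has three steps.

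**Inputs**
- Threshold: (BLQ + missing) / total > 1/3 (Section 3.1). The total is not defined.
- Part A1 cohort size: "each cohort enrolling up to 8 study participants including 1 sentinel participant" (Part A1 Section 2.3).
- Part A cohort size: 3 to 6 evaluable participants (Part A Section 2.3).
- Missing rate per sample, d: not in the documents. It is assumed here to be 10%, 20%, 30% or 40%, independent between participants.
- BLQ values: none, to isolate the effect of missing samples.

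**Step 1. Smallest number missing, k, that triggers the rule (k/n > 1/3)**

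| n | k | k/n | measured values left |
|---|---|---|---|
| 8 | 3 | 37.5% | 5 |
| 6 | 3 | 50% | 3 |
| 5 | 2 | 40% | 3 |
| 4 | 2 | 50% | 2 |
| 3 | 2 | 66.7% | 1 |

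For n = 8, 6 and 5, at least 3 measured values remain, so the 3-value rule would not itself block a summary. In each of these cases the literal text prints the minimum as BLQ although no value was BLQ.

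**Step 2. How often, for a cohort of 8 with all participants counted**

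As written, P(trigger) = P(X ≥ 3) with X ~ Binomial(8, d). For example, at d = 0.2 it is 1 − (0.168 + 0.336 + 0.294) ≈ 0.203.

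If the one-third test used only BLQ values among reported values, then with no BLQ value the statistics would be lost only when fewer than 3 values remain. That probability is P(X ≥ 6).

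| d | as written, P(X ≥ 3) | BLQ-only test, P(X ≥ 6) |
|---|---|---|
| 10% | 0.038 | 0.000 |
| 20% | 0.203 | 0.001 |
| 30% | 0.448 | 0.011 |
| 40% | 0.685 | 0.050 |

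At 20%, 30% and 40% missing, the probability that the rule triggers while at least 3 measured values remain (3 to 5 missing) is 0.202, 0.437 and 0.635. Nearly all the suppression therefore falls on timepoints that could have been summarized.

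**Step 3. Two measured values**

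Take 8 scheduled samples, 6 missing and 2 measured, none BLQ. The missing share is 6/8 = 75%, so the one-third bullet applies and the minimum is BLQ. The two-value bullet also applies and shows the lower of the two values as the minimum. One cell cannot satisfy both. The same happens in a Part A cohort of 4 with 2 missing.

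**The case against.** There is a fair case that the matter is small, and much of it stands.

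- **Withholding a mean when over a third of the samples are unavailable is a defensible convention.** This is true as far as it goes, and the bullets are mostly compatible. Requiring 3 values is a necessary condition, not a promise to summarize whenever 3 exist. Excluding missing values governs calculation, whereas the one-third rule governs display. A reader might infer that the list contradicts itself throughout. It does so only in the two-value case. The convention also does not justify printing BLQ where nothing was BLQ.
- **Dropout need not trigger the rule.** A reader might infer that ordinary discontinuation will remove the secondary PK endpoint at later cycles. That holds only if participants who have left treatment count in the total, which the SAP does not say. If the total means samples due from participants still attending, only undrawn, lost or unreported samples count. The false minimum is still possible then, but the frequencies for a fixed n of 8 do not apply.
- **The endpoint is not blanked.** Suppression is per timepoint and the maximum stays. Section 3.1 of both SAPs provides for listings and individual concentration plots.
- **Safety laboratory data.** A reader might infer that a missing blood sample would turn the lowest platelet count or potassium into BLQ. The documents do not support this as an instruction. Sections 4.2.2 and 4.4 import rules for values that are BLQ. Non-PK data have their own summary list in Section 3.1, with no one-third rule and with minima reported at the precision of the original value. Importing the one-third bullet is a possible reading and no more.

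**Conclusion.** The rule is wrong as written, with minor severity. In Section 3.1 of both SAPs, a concentration timepoint with no BLQ value but more than one third of samples missing would, read literally, lose all statistics except minimum and maximum and would show a false BLQ minimum. With exactly two measured values the instruction also clashes with the neighbouring bullet.

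The trigger counts in Step 1 follow directly from the rule once the total is taken as n scheduled samples. The frequencies of about 4%, 20%, 45% and 68% also rest on assumed missing rates of 10% to 40%, on independence, on no BLQ values and on all 8 participants being counted. They show sensitivity and are not a forecast. No test or decision rule stated in the SAP rests on the affected cells. The finding concerns UCB6114 concentration tables and does not extend to safety laboratory minima.

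**What to change.** In Section 3.1 of both SAPs, replace the one-third bullet with wording such as: *When more than one third of the reported (non-missing) concentrations at a timepoint are BLQ, only the minimum and maximum are presented and other statistics are shown as missing. The minimum is presented as BLQ only if at least one reported value is BLQ.*

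This settles the denominator, since missing samples leave both sides of the ratio, and it removes the two-value conflict. Two measured values with none BLQ give 0/2, so the two-value bullet governs. If one of the two is BLQ, 1/2 exceeds one third and BLQ is then the correct minimum. Sparse timepoints stay under the existing 3-value rule.

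Optionally, add a sentence to Section 4.2.2 (Part A) and Section 4.4 (Part A1) saying that the one-third and minimum rule does not apply to missing laboratory values.

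The cost is one bullet in each SAP and one condition in the summary program. A few more statistics will rest on small numbers, which the n column already shows.
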